Design of Patient Education and Motivation Tool (PEMT): PEMT is a touch screen, computer based interactive health education program designed based on a variety of cognitive-behavioral theories⁴³. PEMT facilitates health information and messages to be adapted depending on the psychosocial elements including attitude, self-efficacy, expectations, personal norms and social influences⁴⁴⁻⁴⁶ (Table1). PEMT has 3 key components including (a) screening gathers individual socio-demographics, knowledge, attitudes and practice through a series of questions; (b) learning component delivers educational material in a structured format. The entire educational material is broken down into series of modules, each module into sub-modules and each sub-module into a series of educational messages. Each message is then presented using various multimedia formats (such as audio, video, text and images) and (c) evaluation component gauges effectiveness of the program by assessing change in knowledge, attitudes and practices of the individuals. The main objective of the PEMT is to

present health information in an interactive tailored manner considering multiple factors influencing health status and health behaviors.

Theory	Purpose	PEMT Learning Component
Information Processing theory ⁴⁷	Information chunking means presenting information as a meaningful unit and short term memory is limited 5 to 9 chunks of information	Each screen has a series of short educational messages
Constructivist Theory ⁴⁸	Present information in a structured format simple to understand	The information is presented in a structured format with a series of several educational modules. Each module is broken down into sub-modules and each sub-module is broken down into a series of educational messages.
Cognitive Flexibility theory ⁴⁹	The information presented should be highly interconnected so that it is relevant to the learner	The information is presented related to the responses to the questions provided during the screening component.
Cognitive Flexibility theory ⁴⁹	Multiple Content Formats should be available including audio, images and text	The information is presented in multiple formats including text, audio, images, and animation. The patients can turn on/off the audio at their own will
Cognitive load theory ⁵⁰	Minimize working memory load	The information on the screen is presented as text enhanced using images and animation to make it easy to understand

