account for health literacy of the individuals. The program will simplify the design and create multiple tailored versions of printed materials instead of using a single standardized version. The tailoring algorithm will be developed based on health literacy levels, prior breast-feeding knowledge and attitude towards breast-feeding practices. For e.g. If a person has low literacy the information will be presented as images and graphics. Similarly information specific to those topics will be presented in which the individual has poor breast-feeding knowledge. Messages will be tailored to perceived breast-feeding concerns. Tailored educational messages might focus on subjects with poor breast-feeding skills and will educate and empower individuals through use of motivational prompts. The program aims to deliver specific messages as computer provides a medium to adopt tailoring with no time lag and multimedia capabilities.

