The subjects will be enrolled at RWMC, Scottsbluff and randomly assigned to either intervention (bilingual Computer based Breast-feeding Educational Support program) or attention control (bilingual breast-feeding printed educational material) groups during the subject's prenatal visit (i.e. anytime during last six weeks of their pregnancy). Once randomized, baseline information will be gathered in both the groups as outlined in Figure5. The difference between the two study groups is that subjects in the intervention (bilingual Computer based Breast-feeding Educational Support program) will record their baseline assessment on a computer and receive tailored breast-feeding education compared to the attention control (bilingual printed breast-feeding educational materials) who will record their baseline information on paper (Figure5) and receive printed breast-feeding educational material. Using self report responses of the individuals in the intervention group (bilingual computer based breast-feeding educational support program), the decision logic and algorithm will process the information and deliver tailored breast-feeding educational messages in varied multimedia formats using a combination of text, images, and animations to account for the literacy levels of the subjects. Appropriate feedback will be given in the form of reinforced educational messages and encouragement and motivational prompts for those using the computer based program. Educational session in both the groups will last for 30 minutes. The first educational session will be performed during the post partum period, one day before the discharge from the hospital followed by week 6, months 3 and 6. Specific individualized interventions, especially during the initial critical 2-6 week period, are needed to prevent deterioration in intention levels for breast-feeding for 6 months and breast-feeding self-efficacy levels within the first 2 weeks postpartum which could lead to the decision to discontinue breast-feeding³¹. Subjects in both the groups will be given telephone reminders for follow up educational sessions. The touch screen computer based Breast-feeding Educational Support program will be placed on a mobile cart in the outpatient clinic of the RWMC, Scottsbluff. A research assistant will be available to guide the subjects in both the intervention (during the use of the tablet pc program) and the control groups (printed educational material) if needed. The breast-feeding educational modules and data collection instruments will be both in English and Spanish.

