
[figure not shown]

Figure5. Flow chart and education sessions in intervention and attention control groups

Description of the variables

The relevant study variables include (i) independent variables, (ii) process variables, (iii) potential confounding variables and (iv) dependent variables (outcomes). All the data gathering instruments will be available both in English and Spanish.

a. Independent variables

The study will have two groups: intervention group will receive bilingual Computer based Breast-feeding Educational Support program while attention control group will receive bilingual printed breast-feeding educational materials

b. Process variables

Variables impacting breast-feeding duration include;

Breast-feeding Knowledge: The Breast-feeding Questionnaire (BKQ)²⁴ was used in a randomized clinical trial of education and support for adolescent mothers²⁴. Items from two tests of breast-feeding knowledge^{55, 56}, were combined to provide a 30-item measure. Nineteen items developed for use with adolescent girls as a measure of laypersons' breast-feeding knowledge⁵⁵, were used in combination with 11 items from the Breast-feeding Knowledge Questionnaire (BKQ) ⁵⁶. The questionnaire includes multiple-choice and true-false items on the components of breast milk, colostrums, weaning and breast-feeding techniques. Reliability (internal consistency alpha coefficient-KR20) of the measure was .70 (Appendix B).

Breast-feeding Attitude/Beliefs: The Breast-feeding Attrition Prediction Scale (short-form) [BAPT] Spanish and English^{38, 39}. This 35 item scale is based on theory of planned behavior⁵⁷. It includes 4 sub-scales:1) positive breast-feeding sentiment (PBS); 2) negative breast-feeding sentiment (NBS); 3) social support and professional support (SPS) and 4) perceived behavioral control (PBC) for breast-feeding. Two International Board Certified lactation consultants reviewed the revised BAPT and judged the items to be both relevant and appropriate. Reliability was good with sub-scales scoring .67-.88 Cronbach's alpha. The overall scale demonstrated predictive validity by differentiating sustained breast-feeding at 8 weeks ³⁸ (Appendix C)

Perceived norms: Is described as the perceived pressure to perform a behavior³⁴. Social pressure will also be measured by a sub-scale of the revised BAPT. It is critical that perceived norms be measured for Hispanic

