Acceptance of Computer-based Breast-feeding Educational Support program: We will adapt and use previously published questionnaire used to assess acceptance of computer based asthma educational program⁴⁶ (Appendix F). Feedback will be gathered on ease of use of program, navigation patterns, and feedback during the program, future use of program and recommendation to others to use the program. Usage data analysis will help to understand learning patterns during use of the computer program by gathering the amount of time an individual spent on viewing the educational modules.

d. Potential Confounders

Socio-demographics: Include age, income levels, employment status, and education level, smoking status, prior pregnancies and previous history of breast-feeding. Information is also gathered about prior use of computers, its frequency of usage prior use of internet and sources of health information (Appendix G). Health literacy is the ability to perform basic reading and numerical tasks required to function in the health care environment⁶⁵. Studies have shown an association between limited health literacy and worse health outcomes such as poorer knowledge about health conditions^{66, 67}. The 3 health literacy screening questions, which performed optimally in a previous study⁶⁸, will be used to assess health literacy assessments of Hispanic rural women (Appendix H) and include: "How often do you have someone (like a family member, friend, hospital/clinic worker or caregiver) help you read hospital materials?" (Help Read), "How often do you have problems learning about your medical condition because of difficulty understanding written information?" (Problems Reading), and "How confident are you filling out forms by yourself?" (Confident with forms). Responses will be scored on a Likert scale from 0 to 4 and were asked to choose between all of the time, most of the time, some of the time, a little of the time or none of the time⁶⁸.

In addition, Newest Vital Sign (NVS) consisting of a nutrition label with 6 accompanying questions to assess literacy will be used⁶⁹. It takes approximately 3 minutes to administer, and is meant to allow healthcare providers to make a quick assessment of patients' literacy, which can then allow them to adapt communication to achieve better outcomes. It assesses literacy and numeracy, and is available in both English and Spanish versions. The

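### Baseline is gathered after allocation, on computer in one arm and paper in the other, and at least five of nine exclusions can only arise after randomisation, with no analysis set named

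*Combined protocol and SAP*

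**What the plan says.** Section IV, Research Design and Methods, assigns women at random at a prenatal visit and places baseline after that step: "prenatal visit (i.e. anytime during last six weeks of their pregnancy). Once randomized, baseline information will be gathered in both the groups". Intervention women "will record their baseline assessment on a computer"; controls are those "who will record their baseline information on paper". Data Collection procedures puts baseline at the same enrolment visit and does not reverse the order. The same part of section IV sets the start of education: "The first educational session will be performed during the post partum period, one day before the discharge from the hospital".

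On-screen questions are part of the program. The PEMT design section describes its first component as "a) screening gathers individual socio-demographics, knowledge, attitudes and practice through a series of questions", and the Tailoring paragraph adds: "The tailoring algorithm will be developed based on health literacy levels, prior breast-feeding knowledge and attitude towards breast-feeding practices".

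Subject eligibility lists nine exclusions. Five concern maternal ICU admission in the hospital stay, birth weight, bilirubin, NICU admission and stillbirth. A sixth concerns gestation under 36 weeks.

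Statistical Analysis tests baseline differences between arms, compares the 6-month primary outcome by chi-square test, and in exploratory models adds confounders that differ between arms at the 0.20 level. It names no analysis set. Sample Size Justification gives 23 per group, raised to 27 for 15% attrition. The only mention of intention to treat, in the Background, describes another study.

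Figure 5, captioned "Flow chart and education sessions in intervention and attention control groups", is not visible in the text available and may show the timing of these steps.

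**The concern.** Baseline should describe the women before allocation can influence their answers. Here a woman may know her arm when she answers, and she answers in the mode belonging to that arm. A baseline difference could then be a true chance imbalance, an effect of mode, or an effect of knowing the allocation, and the planned tests cannot tell these apart. The covariate screen acts on such differences.

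The exclusions raise a different problem. A criterion that can be met only after randomisation does not select who enters the trial; it removes women from a randomised comparison. If removal depends in any way on arm, the groups analysed are no longer the groups randomised. Even if it does not, the numbers fall, and the sample size has no visible reserve for that.

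**Working it through.** **1. Which exclusions come after randomisation.** Randomisation is in the last six weeks of pregnancy.

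| Exclusion | Earliest it can be known |
|---|---|
| Mental or physical difficulty using the program; no telephone follow-up; other breast-feeding studies | Enrolment |
| Gestation under 36 weeks | Largely at birth; partly checkable at enrolment |
| Maternal ICU admission; birth weight; bilirubin; NICU admission; stillbirth | At or after birth |

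That is five for certain, or six if gestation is counted. This counts criteria, not women; the documents give no rate.

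**2. The plan's own sample size.** Inputs from Sample Size Justification: 0.3 against 0.7, two-sided 0.05, Pearson chi-square. Power is the sum of the binomial probabilities of all result pairs with uncorrected chi-square above 3.841. At 23 per group it is 0.809, which agrees with the stated power of at least 0.8. At 22 it is 0.778 and at 21 it is 0.748.

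**3. Reserve after attrition.** 27 × 0.85 = 22.95 per arm, against 23 needed. Evaluable numbers vary by chance, so I averaged exact power over independent Binomial(27, 0.85) counts in each arm: about 0.797.

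**4. If women with birth events are removed on top of the 15%.** Let e be the assumed fraction removed. Evaluable counts are Binomial(27, 0.85 × (1 − e)). If the 15% is instead meant to cover all losses, the room left for follow-up attrition is 1 − 0.85/(1 − e).

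**5. If these women are kept.** Evaluable counts are Binomial(27, 0.85). If they respond like the others, power stays at 0.797. If the program has no effect in them (0.3 in both arms), the intervention proportion becomes 0.70 − 0.40e, that is 0.692, 0.68 or 0.66.

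| Assumed e | Power, removed | Room for attrition if the 15% is total | Power, kept, no effect in them |
|---|---|---|---|
| 2% | 0.789 | 13.3% | 0.780 |
| 5% | 0.776 | 10.5% | 0.753 |
| 10% | 0.754 | 5.6% | 0.705 |

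Keeping them protects the randomised comparison; it does not guarantee more power.

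**6. The baseline screen.** Take a continuous health-literacy score, 27 per group, two-sample t-test with 52 degrees of freedom and noncentrality d × √(27/2), with no true imbalance. The documents give no mode effect, so d is assumed.

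| Assumed pure mode effect (SD) | Passes the 0.20 screen | Significant at 0.05 |
|---|---|---|
| 0 | 20% | 5% |
| 0.2 | 31% | 11% |
| 0.3 | 43% | 19% |
| 0.5 | 71% | 44% |

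These are rates of covariate selection and of apparent baseline imbalance. They do not measure bias in a treatment estimate.

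**The case against.** **The baseline part has limited reach, and this stands.** The primary test uses no baseline value. Knowledge, self-efficacy, attitudes, norms and intent are listed as process variables, not as confounders feeding the 0.20 screen. Most listed confounders are factual, such as age, education and prior pregnancies. The plausible route is health literacy, which includes the self-rated item "How confident are you filling out forms by yourself"; its companion, the Newest Vital Sign, is a performance test. A reader might infer that the knowledge and self-efficacy results are distorted as changes from baseline. Statistical Analysis states no change-from-baseline test, so the documents do not support that.

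**One mode for everyone is not clearly better, and this stands.** A reader might infer that a common mode is required. On-screen screening feeds the tailoring, and Table 1 says the program prompts on correct answers and reinforces messages on incorrect ones. The documents do not show that controls could use the tablet without that feedback.

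**Most exclusions precede education, and this stands in part.** The first session is the day before discharge, so the program can hardly cause most of these events. But some, such as a high bilirubin, could follow that session, and no blinding of whoever applies the exclusions is described. A reader might infer that the primary result is biased; the documents support only that it could be.

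**Enlarging the trial.** A reader might infer that 58 or 62 women should be randomised, to offset 5% or 10% removals. Those totals assume the women are removed. If they are kept and respond like the others, 28 per arm already gives 0.813. If the program has no effect in them, 29 per arm at 5% and 31 at 10% give only 0.784 and 0.764. Neither total fits an analysis that keeps them.

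**Target population.** Stable infants are a deliberate focus of the eligibility section. That argues for keeping the restricted analysis visible, not for leaving the analysis set unstated.

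**Conclusion.** Both parts hold on the visible text and should be fixed, with medium confidence because Figure 5 cannot be seen.

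The order and mode of baseline affect the between-arm baseline tests and the exploratory covariate choice, chiefly through health literacy. The size depends on an unknown mode effect; for an assumed 0.2 to 0.5 SD, selection at the 0.20 level rises from 20% to between 31% and 71%.

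The exclusions, as written, remove randomised women under an analysis plan that does not say who is analysed. The main cost is numbers: from about 0.797 to between 0.789 and 0.754 for an assumed further 2% to 10%. Bias is possible if an event follows the first education session or if exclusions are applied with knowledge of arm. The power figures rest on the plan's own 0.3 and 0.7, independent losses, and 15% attrition that does not already include birth events, which the plan leaves unstated.

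**What to change.** 1. At the same prenatal visit, complete the baseline questionnaires before allocation is revealed. This reorders two steps within one visit. A single mode, for example paper for all with answers keyed into the program for women then assigned to it, is an option. Its price is about 27 paper baselines to key and the loss of on-screen self-entry at baseline in the intervention arm.

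2. Define the primary analysis as all randomised women with a 6-month feeding outcome, in the arm assigned, without removing women for events first seen after randomisation. A stillbirth leaves no feeding outcome; report stillbirths and the other birth-related events by arm. Give the analysis restricted to women meeting the birth criteria as a sensitivity analysis. The price is a population slightly wider than stable infants and possibly lower power (0.753 or 0.705 at an assumed 5% or 10%, against 0.797) if the program does not work in these women. Follow-up vouchers are at most 4 × $15 = $60 per retained woman. For 5% or 10% of 54 (2.7 or 5.4 women) that is up to $162 or $324, plus staff time.

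3. State whether the 15% covers birth-related losses, and restate the power accordingly. This costs a few sentences.

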mothers since familism is an important cultural social structure in which the needs of the family as a group are more important than the needs of any individual family member and may include nutrition behaviors⁵⁸. This strong cultural value in Mexican American families embodies social support within the extended family^{59, 60} (Appendix C)

Breast-feeding Self-Efficacy: Self-efficacy is the personal belief that one can effectively perform a given behavior and that the behavior will result in the desired outcome. Self-efficacy has also been identified as a modifiable psychosocial variable in predicting behavior performance⁶¹, including sustained breast-feeding⁶². We will use Breast-feeding self-efficacy scale short form (BSES-SF). The BSES-SF is a 14-item 5-point Likert scale questionnaire that has response categories that range from 1 = not at all confident to 5 = always confident. An internal consistency alpha coefficient of .97 was obtained for the revised total scale. Predictive validity was demonstrated by significantly higher breast-feeding self-efficacy scores in breast-feeding mothers compared to bottle-feeding mothers at 4 ($p < .001$) and 8 ($p < .001$) weeks postpartum. Content validity of 86% was established with a review by an expert panel⁶² (Appendix D)

Intent to breastfeed for 6 months: -is defined as readiness to engage in a behavior. It will be measured by an intention question related to the mother's perceived intent to breastfeed for the recommended 6 months. The question has been developed based on Fishbein & Ajzen's guidelines³⁴ and is "How likely is that you intend to breastfeed for 6 months is measured by a 7 point Likert scale (extremely likely to extremely unlikely)?"

c. Dependent Variables

Primary outcome: Primary outcome is partial (combined formula and breast milk feeding) or exclusive breast-feeding at six months⁶³ and will be assessed using breast-feeding assessment questionnaire⁶⁴ (Appendix E). The questionnaire will also assess information about the timing of introducing solid food during the first six months. Exploratory analysis will also be performed to determine the proportion of Hispanic rural women who continue to do exclusive breast-feeding at six months in both the intervention (bilingual computer based breast- feeding educational support program) and control (bilingual printed breast-feeding educational materials)

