Baseline data will be gathered during the enrollment prenatal visit (anytime during last six weeks of pregnancy) and follow up data will be collected on postpartum day 3, week 6 and months 3 and 6 resulting in overall five data collection time periods. The postpartum day 3 data collection will be done over the telephone while other follow up data collection including week6 and months 3 and 6 will be done when the individuals in both the groups will come to the hospital for follow up educational sessions. Almost all women who initiate breast-feeding plan to continue for at least 6 weeks; however, one of every five women quits breast-feeding within the first days after delivery⁷³. This finding supports the notion that 2–4 weeks postpartum is a vulnerable period for breast- feeding cessation⁷⁴. Baseline evaluation will be done during the prenatal visit (last trimester). The research assistant will schedule a follow up interview to administer the study questionnaires at a convenient time over the telephone. Subjects will receive gift vouchers worth \$15 for baseline and for every follow up postpartum visit (Table2).

Pre and Post educational Session data collection	Baseline	Day 3	Week 6	Month 3	Month 6
Socio-demographics	X				
Health Literacy	X				
Breast-feeding Knowledge	X	X	X	X	X
Breast-feeding self-efficacy	X	X	X	X	X
Intent to Breast-feed	X	X	X	X	X
Breast-feeding attitudes	X	X	X	X	X
Perceived norms	X	X	X	X	X
Program acceptance	X				X

Table2. Data Collection in intervention and attention control groups

Informed Consent

[name] (Consultant) is a bilingual and certified Spanish translator and will administer the informed consent and assent forms at the RWMC, Scottsbluff after the eligible subjects have agreed to participate in the study. The research staff members will read the UNMC IRB-approved consent and assent forms to subjects describing the study, the measures used by the researchers to protect the confidentiality of the responses, and the voluntary nature of the study. Those who agree to participate will be asked to sign the consent and the assent forms as appropriate. The research staff member will countersign the consent and the assent forms and copies will be given to the participant.

Data Entry and Quality Assurance

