In the first step of exploratory analysis, we will present a table to summarize the distribution of all variables, including outcomes, confounding, and process variables. This table will also serve the purpose of quality control of the original data, to mine missing data patterns and outliers. The distributions of the continuous outcomes will be explored for normality and transformations will be used if warranted. Continuous variables will be summarized using means, medians, standard deviations and ranges while categorical variables will be examined using frequencies and percentages. Exploratory analysis on process variables will be used for post-hoc analysis. Inter-rater reliability of knowledge, attitudes/beliefs, self-efficacy and intent to breast feed will be examined using the kappa statistic.

Sample Size Justification

The optimum number of participants for a focus group is typically 6-10 people with similar backgrounds who participate in the interview for one to two hours may vary⁵². The number generally suggested as being manageable is between six and ten participants as smaller groups show greater potential and large enough to gain a variety of perspectives and small enough not to become disorderly or fragmented⁵². For the intervention effect analysis, a comparison of two independent binomial proportions using Pearson's Chi-square statistic with a two-sided significance level of 0.05, a sample size of 23 per group achieves a power of at least 0.8 when the proportion with partial breast-feeding at 6 months are 0.3 for the control group and 0.7 for the intervention group. To account for anticipated attrition of 15%, the sample size will be increased to 54 subjects (27 per group). This is a pilot study to explore the possibility of promoting breast-feeding using computer based breast-feeding tailored educational program among Hispanic rural women.

Statistical Analysis

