Baseline characteristics will be summarized by intervention group. A chi-square test will be used to compare baseline categorical variables between the intervention and control groups and a t-test will be used for continuous variables. The primary outcome of proportion partial or exclusive breast-feeding at 6 months will be compared between groups using a Chi-square test. The primary outcome will be assessed at 6 months; however, we will also conduct these analyses at 6 weeks and 3 months. A generalized linear mixed model using a binomial distribution and logit link function will be used to examine partial breast-feeding at day 3, week 6 and months 3 and 6 postpartum, with intervention group as a fixed effect and subject as a random effect using a Variance Components covariance structure. In exploratory analyses, covariates will be added to the model to adjust for confounders that differ significantly between both the intervention and attention control groups at the 0.20 level of significance. Similar analyses will be conducted to examine exclusive breast-feeding. Breast-feeding knowledge, self-efficacy, will be compared between groups using a t-test. In exploratory analyses, a general linear mixed model with intervention group as a fixed effect and subject as a random effect using an AR (1) covariance structure will be examined. Covariates will be added to the model to adjust for confounders that differ significantly between both the intervention and attention control groups at the 0.20 level of significance (Table3).

Variables Assessment	Variable types	Data Analysis	Anticipated Outcomes
Focus groups	Qualitative	Framework analysis	Breast-feeding educational modules and functionality of the computer based program established
Socio-Demographics	Continuous & Categorical	T test for continuous and Chi-square tests for categorical variables.	Distribution of population characteristics
Intent to Breast-feed	Categorical	Chi-Square test	Assess intent to breast-feed

Breast-feeding knowledge	Continuous	T test	Improve Breast-feeding knowledge (intervention)
Breast-feeding attitudes and beliefs	Continuous and categorical	T test for continuous and Chi-square tests for categorical variables.	Change Breast-feeding related attitudes and beliefs
Breast-feeding perceived norms	Continuous and categorical	T test for continuous and Chi-square tests for categorical variables.	Change Breast-feeding related behavior

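### Intent to breast-feed is an ordered 7-point item, but Table 3 assigns it a chi-square test with no order-using test and no cut-point; on seven levels this loses roughly 30-60% of rank-sum power under assumed distributions.

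*Combined protocol and SAP*

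**What the plan says.** The process-variables part of Research Design and Methods defines intent as a single question: "you intend to breastfeed for 6 months is measured by a 7 point Likert scale (extremely likely to extremely unlikely". Table 2 schedules it at baseline, day 3, week 6, month 3 and month 6 ("Intent to Breast-feed X X X X X"). The design section gives the question a direction, since the sessions are meant to "prevent deterioration in intention levels for breast-feeding for 6 months".

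The row for intent in Table 3 reads "Intent to Breast-feed Categorical Chi-Square test". The Statistical Analysis text does not mention intent. It covers other variables: "Breast-feeding knowledge, self-efficacy, will be compared between groups using a t-test", with a general linear mixed model described next as exploratory, and a binomial mixed model for breast-feeding status. Exploratory Data Analysis names intent only for a kappa statistic, and says of the whole group of process variables: "Exploratory analysis on process variables will be used for post-hoc analysis". The plan gives no grouping of the seven levels, no cut-point, no order-using test and no time point for the intent comparison.

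**The concern.** A Pearson chi-square test on seven levels gives the same result if the levels are shuffled. It therefore spreads its power over every kind of difference between the arms, although the protocol asks about movement in one direction. Self-efficacy, which is built from 5-point Likert items, gets a t-test that uses direction; intent does not.

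Table 3 can also be read as implying a two-level split. The cut would then have to be chosen, and nothing stops that from happening after the data are seen. On either reading, a consequential choice is left open for a variable that the study's framework treats as the main determinant of behaviour. The stake is a missed shift in intent in a pilot meant to inform a larger trial.

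**Working it through.** **Inputs from the documents.** Seven ordered levels (process variables); chi-square test (Table 3); 23 evaluable per arm, two-sided 0.05, and primary-outcome rates of "0.3 for the control group and 0.7 for the intervention group" (Sample Size Justification). The 0.05 level is stated for the primary comparison and is assumed here for intent.

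**Inputs assumed.** The documents give no distribution or effect size for intent. Six control distributions were used (uniform, bell-shaped, U-shaped, skewed low, and two degrees of skewed high), with a proportional-odds shift between arms.

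**The plan's own figure.** Exact enumeration of the uncorrected Pearson test at 23 per group, 0.3 against 0.7, gives power 0.809, so the stated power of at least 0.8 reproduces. For attrition, 23/0.85 = 27.06, against the 27 stated. No power is stated for intent.

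**Sparseness.** With equal arms, the expected counts in one arm sum to 23 over seven columns. Since 4 x 5 = 20 <= 23 < 25 = 5 x 5, at most four columns can reach 5 and at least three fall below. In the simulations, 5.1-6.2 of the seven columns fell below on average.

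**Reference effect.** The odds ratio implied by the primary-outcome assumption is (0.7/0.3)/(0.3/0.7) = 5.44.

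**Power with all seven levels kept**, 23 per arm, 10,000 runs under the null and 6,000 per effect. Ranges are over the six distributions, and relative loss = (rank-sum - chi-square)/rank-sum:

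| Odds ratio | Chi-square | Rank-sum | Relative loss |
|---|---|---|---|
| 1 (null) | 0.028-0.043 | 0.048-0.053 | n/a |
| 2 | 0.085-0.108 | 0.236-0.262 | 58-64% |
| 3 | 0.191-0.249 | 0.473-0.546 | 53-60% |
| 4 | 0.309-0.413 | 0.660-0.739 | 44-53% |
| 5.44 | 0.440-0.595 | 0.794-0.884 | 33-45% |
| 7 | 0.564-0.728 | 0.877-0.947 | 23-36% |

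A separate simulation with 40,000 runs per setting and its own six distributions agrees. For odds ratios 2 to 5.44 the loss is 34-64% at 23 per arm and 27-63% at 27 per arm. One case from it (skewed high, odds ratio 4, 23 per arm): (0.709 - 0.353)/0.709 = 50%.

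**Power if dichotomised** (uncorrected Pearson, all six cuts, 23 per arm). At odds ratio 3, the worst cut gives 0.003-0.273 and the best 0.449-0.461. At 5.44, the worst gives 0.003-0.472 and the best 0.777-0.814.

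**Supportive model.** A proportional-odds model adjusted for baseline intent was tried on uniform and strongly skewed distributions, with an assumed latent correlation of 0.5. Null rejection was 0.061 and 0.056 (3,000 runs each). Power at odds ratio 3 was 0.656 and 0.581, against 0.555 and 0.486 for rank-sum (1,500 runs each). There was no convergence failure in the 9,000 data sets.

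**The case against.** **The size depends on the assumed shift.** Proportional odds favours the rank-sum test. Of four non-proportional patterns tried, two still gave losses of 27-44%, but in the other two chi-square won. At 23 per arm it had 0.476 against 0.117 when mass was added at both extremes, and 0.626 against 0.408 when movement was only from the middle to the top. For a very large shift (odds ratio 8) the loss shrinks to 12-30% over 23-27 per arm. This stands: the loss applies to a consistent shift in intent, which is what the design section describes.

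**Late answers may cluster at the ends.** By months 3 and 6 many mothers may have stopped or nearly reached six months. That is an inference, not something the documents state. With 60% and 30% of control answers at the two ends and 2% in each middle level, chi-square has 0.65 against 0.83 at odds ratio 5.44, a loss of about one fifth. With every answer at an end, the tests coincide. Clustering at the ceiling works the other way, with a loss of about 56% at 5.44.

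**A two-level split may have been intended.** Table 3 gives the same label and test to breast-feeding status, which is analysed as a proportion. A cut near the median costs only about 3-26% of rank-sum power for odds ratios 2 to 5.44. But no cut is stated, and a poor one is very costly.

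**It matters little.** Intent is exploratory in a pilot, no power is claimed for it, and even rank-sum has only about 50% power at odds ratio 3. This limits the importance of the point but does not remove it, because Table 3 names a specific test and an analyst following it would run the weaker one. Testing at several visits adds no more multiplicity than the planned chi-square would.

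**Conclusion.** The concern holds. The mismatch needs no assumption: the item is ordered, the named test ignores order, and neither a cut-point nor an order-using test is given. The size is conditional. For a consistent shift with odds ratio 3 to 5.44, at 23 per arm with all seven levels kept, the relative loss is 33-60% over the distributions in the table. It is smaller for very large shifts or end-clustered answers, and reversed for some patterns that are not a shift. The seven-level chi-square is mildly conservative under the null, so false positives are not the issue. The primary analysis and sample size are untouched. This is a change worth making, not one on which the trial depends.

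**What to change.** In Table 3, reclass intent as ordinal and replace the chi-square with a Wilcoxon rank-sum test between arms at each post-baseline assessment in Table 2 (day 3, week 6, months 3 and 6). Say which of these is of main interest.

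Add one sentence for a supportive proportional-odds model on group, adjusted for baseline intent, reporting the common odds ratio with its 95% confidence interval. Keep rank-sum as the named test: with about 46 evaluable subjects the model's test ran slightly liberal, and the model could fail to converge if answers pile up in one level. If a two-level summary is also wanted, state its cut before the data are seen.

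The cost is one table row, a sentence or two and a little more analysis. Intent is already collected at baseline and all four follow-ups. The change reduces the power problem but does not remove it.
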